The CCSS database represents the only chance in which the issue of the breast cancer molecular subclass prevalence, in the setting of previous thoracic radiation, could possibly be addressed. If any single institution attempts to do this, there would not be enough cases to draw a statically significant conclusion. Fortunately, there are 54 cases within the CCSS database, and this is sufficient to determine if the 5 molecular subtypes are evenly distributed, or predominately composed of 1 or 2 subtypes. In the most diffuse scenario, if there are at least 10 samples per subtype (5), there will be a >80% power to detect a 2-fold difference between any of the two groups using Chi-squared analysis. A coefficient of variation of 50% and alpha = 0.005 (.05/10, to adjust for 10 comparisons between 5 groups) will be used for the calculations. Since we expect there to be 50% with the Luminal A subtype designation, there will be even greater power to make this conclusion statistically valid. It should be iterated, though, that regardless of statistical power, this is a retrospective study and the large number of subjects from the CCSS provide the only means for attempting to answer this scientific question.

Figures:

Hierarchical clustering of 115 tumour tissues and seven non-malignant tissues using the "intrinsic" gene-set. (A) A scaled-down representation of the entire cluster of 540 genes and 122 tissue samples based on similarities in gene expression. (B) Experimental dendrogram showing the clustering of the tumours into five subgroups. Branches corresponding to tumours with low correlation to any subtype are shown in grey. (C) Gene cluster showing the *ERBB2* oncogene and other co-expressed genes. (D) Gene cluster associated with luminal subtype B. (E) Gene cluster associated with the basal subtype. (F) A gene cluster relevant for the normal breast-like group. (G) Cluster of genes including the oestrogen receptor (*ESRI*) highly expressed in luminal subtype A tumours. Scale bar represents fold-change for any given gene relative to the median level of expression across all samples. PNAS, July 8, 2003, vol. 100, no. 14, 8418–8423. Copyright (2003) National Academy of Sciences, USA.

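### The >80% power claimed for a chi-square test of a 2-fold difference between two subtypes (10 samples each, alpha 0.005) is wrong: with exactly 10 v 10 the power is at most 38%

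*Protocol*

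**What the plan says.** The power statement is in the last paragraph of Statistical and Analytic Plans in the protocol. It starts from the available material ("Fortunately, there are 54 cases within the CCSS database") and calls this enough to tell whether the five subtypes are evenly spread or dominated by one or two. It then takes the most diffuse case, with at least 10 samples in each of five subtypes, and claims that "there will be a >80% power to detect a 2-fold difference between any of the two groups using Chi-squared analysis". The inputs follow: "A coefficient of variation of 50% and alpha = 0.005 (.05/10, to adjust for 10 comparisons between 5 groups". The next sentence adds that the expected 50% Luminal A share makes the power greater still.

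No base proportion is given, no sidedness, and no statement of which variable differs 2-fold. Earlier in the same section the planned test of subtype distribution is a different one: a chi-square comparing the 54 study cases with the 1,619 controls. Specific Aim 1 expects shares of about 50% Luminal A, 20% Luminal B, 20% Basal and 10% Her2.

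**The concern.** Test, group size, effect ratio, alpha and power are all stated, so the claim can be checked without an SAP. Two things look wrong on sight. Ten per group at alpha 0.005 is very small for comparing proportions. And a coefficient of variation describes a continuous measurement; a chi-square test of counts does not use one.

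This is the only power figure in the protocol, and it directly follows the statement that 54 cases are sufficient. The study's leading hypothesis is that irradiated and spontaneous cancers have the same subtype mix, so a non-significant result would be taken as support. A reader who believes the comparison had more than 80% power would give such a result too much weight.

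**Working it through.** **Inputs from the protocol.** n = 10 per subtype, five subtypes, 54 cases in all; "a 2-fold difference between any of the two groups"; "using Chi-squared analysis"; alpha = 0.05/10 = 0.005. **Assumptions.** Two-sided test; proportions p v 2p with p from 0.02 to 0.50, because no base rate is given.

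**1. The stated figure, most favourable case.** No 2-fold difference in proportions exceeds 50% v 100%. The critical value of chi-square (1 df, 0.005) is 7.879. For a 2x2 table, X² = N(ad − bc)² / (product of the four margins).
- 10/10 v 5/10: X² = 20 × 50² / (10 × 10 × 15 × 5) = 6.667, p = 0.0098. Not significant.
- 10/10 v 4/10: X² = 20 × 60² / (10 × 10 × 14 × 6) = 8.571, p = 0.0034. Significant.

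The test therefore rejects only if the 50% group shows 4 or fewer of 10. Power = P(Bin(10, 0.5) ≤ 4) = 386/1024 = 37.7%. With Fisher's exact test it is 17.2%. The claimed >80% is not reproduced.

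**2. Other 2-fold pairs**, exact Pearson power over all 11 × 11 tables, 10 v 10, alpha 0.005:

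| Pair | Power |
|---|---|
| 10% v 20% | 0.2% |
| 20% v 40% | 2.2% |
| 30% v 60% | 5.2% |
| 40% v 80% | 12.9% |
| 45% v 90% | 21.9% |
| 50% v 100% | 37.7% |

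**3. The four spare cases.** Five subtypes of 10 use 50 of the 54 cases. If the other four all fall in the 100% group (10 v 14), 5/10 v 14/14 gives X² = 24 × 70² / (10 × 14 × 19 × 5) = 8.84 (significant) and 6/10 v 14/14 gives 24 × 56² / (10 × 14 × 20 × 4) = 6.72 (not). Power = P(Bin(10, 0.5) ≤ 5) = 638/1024 = 62.3%. For the same pair, 11 v 11 gives 50%, 12 v 12 gives 61%, and 14 v 10 (spare cases in the 50% group) gives 40%. All stay below 80%.

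**4. Using the coefficient of variation.** Two-sample t-test, 10 per group, 18 df, two-sided alpha 0.005, critical t = 3.197, noncentrality d × √(10/2). Take the means as 1 and 2.
- Coefficient of variation 50% in each group, raw scale: SDs 0.5 and 1, root mean square √0.625 = 0.791; d = 1.265, noncentrality 2.83, power 39%.
- Coefficient of variation 50%, log scale: SD = √ln(1.25) = 0.472; d = ln 2 / 0.472 = 1.467, noncentrality 3.28, power 55%.
- SD 0.5 in both groups: d = 2, noncentrality 4.47, power 88%. The larger group's coefficient of variation is then 0.5/2 = 25%.

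**5. Dropping the adjustment.** At alpha 0.05 the 50% v 100% chi-square has 83% power and the log-scale t-test 87%. The protocol states 0.005.

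**6. The comparison the plan does make**, 54 cases v 1,619 controls. Simulated Pearson chi-square; assumptions: four classes at 50/20/20/10 in controls, 3 df, alpha 0.05, the other case shares rescaled proportionally.

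| Share among cases | Power |
|---|---|
| Basal 40% (controls 20%) | about 81% |
| Basal 30% | about 29% |
| Luminal A 30% (controls 50%) | about 72% |
| Luminal A 35% | about 46% |
| Her2 20% (controls 10%) | about 47% to 48% |

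If the Basal excess comes from Luminal A alone (30/20/40/10), the first figure is about 88% to 89%.

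**The case against.** **The protocol says at least 10, not exactly 10.** This stands as a limit on the number, not on the conclusion. A reader might infer that no pairwise subtype comparison in this study can exceed 38%. The documents do not support that. Under the expected mix, 54 cases give about 27 Luminal A and 11 each of Luminal B and Basal. For 27 v 11 at the extreme 50% v 100%, power is about 97% when the smaller group is at 50% and about 65% the other way round. So the remark about greater power is right in direction for pairs with Luminal A. It does not extend to any pair: Her2 at 10% would have about 5 cases, below the 10 that the power sentence requires.

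**One reading gives more than 80%.** A t-test with the SD at half the smaller mean reaches 88%, and the study does measure gene expression. But the sentence names a chi-square test, and this reading breaks the stated 50% coefficient of variation in one group. The readings that keep it in both groups give 39% and 55%.

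**The harm is limited.** A reader might infer that 54 cases cannot answer the study's main question. That does not follow. The planned distribution test is against 1,619 controls and has reasonable power for large shifts. A goodness-of-fit test of 54 cases against an even five-way split, if the truth is 50/20/20/10/0, has more than 99% power even at 0.005. The number of cases is set by available tissue, and the protocol itself says that the study is worth doing whatever its power. All of this stands. It is a reason to state the power correctly; it does not make the printed figure right.

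**Conclusion.** The >80% figure is wrong as written. For a two-sided Pearson chi-square at alpha 0.005 with exactly 10 v 10, no 2-fold difference has more than 38% power. With at least 10 in every subtype and 54 cases in all, the best allocation reaches 62%. These ceilings need no assumed base rate, since 50% v 100% is the extreme case; the 2% for 20% v 40% and 13% for 40% v 80% are illustrations only. The stated coefficient of variation does not belong to the named test, and applying it consistently in a t-test does not rescue the claim.

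The conclusion is confined to this power statement. It is neither a 38% limit on every subtype pair nor a finding that the comparison with controls is inadequate.

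**What to change.** Delete the sentence claiming more than 80% power, and the coefficient of variation with it. In their place give power for the planned chi-square of 54 cases against 1,619 controls, and state the assumptions: classes and control shares, degrees of freedom, alpha, and how the other shares change when one rises or falls. The figures in step 6 of the working can be used under the assumptions listed there; redo them with 4 df if the normal-like class is kept as a fifth category.

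If pairwise subtype comparisons are retained, say which variable is compared and give power for the group sizes and base rates assumed. Do not insert a general statement of at most 38%. Limit the remark about greater power to pairs that include Luminal A.

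Cost: protocol wording only, with no extra samples. The stated power becomes less favourable.
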